17.1.2. Serious Adverse Events

Participants who experienced at least 1 SAE within 28 days after any dose, from dose 1 until 28 days post last dose and during the entire study period will be listed.

The number and percentage of participants with any SAE and SARs between Day 57 (28 days post second injection) to Day 168 and from 28 days after third vaccination up to Day 365 will be summarised by treatment group and by SOC and PT.

17.2. Deaths

If any subjects die during the study, the information will be presented in a data listing.

17.3. Safety Laboratory Evaluations

Clinical laboratory results will be included in the reporting of this study for Haematology, Serum Chemistry and Urinalysis. A list of laboratory assessments to be included in the outputs is included in Appendix 2 of the protocol, Table 6. Presentations will use units, as provided by the labs.

Protocol-specified clinical laboratory tests will be summarized by treatment using descriptive statistics. Clinical laboratory data collected during study conduct, which were not required per protocol, such as for special testing to evaluate an AE, will be listed separately and not summarized.

Quantitative laboratory measurements reported as “< X”, i.e. below the lower limit of quantification (BLQ), or “> X”, i.e. above the upper limit of quantification (ULQ), will be converted to X for the purpose of quantitative summaries, but will be presented as recorded, i.e. as “< X” or “> X” in the listings.

The following summaries will be provided for laboratory data:

- Observed and change from baseline by visit for each treatment (for quantitative measurements)
- Incidence of abnormal values according to normal range criteria
- Listing of lab results outside the normal range

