9.4.1 Safety Analysis

The percentage of participants with at least one solicited AE (local and systemic), with at least one unsolicited AE, and with any AE during the 7-day or the 28-day follow-up period will be tabulated after each vaccination and overall. Similar tabulation will be done for Grade 3 events, any AESIs, any MAAEs, any AEs considered related to the vaccination and any Grade 3 AEs considered related to vaccination.

The percentage of participants reporting each individual solicited local and general AE during the 7-day follow-up period will be tabulated over the three doses.

The percentage of participants with unsolicited AEs, including AESIs, MAAEs and SAEs within 28 days after any doses will be tabulated by treatment and by Medical Dictionary for Regulatory Activities (MedDRA) preferred term. Similar tabulation will be done for Grade 3 unsolicited AEs and for Grade 3 and causally related unsolicited AEs and for unsolicited AEs causally related to vaccination.

The number of participants who experienced at least one SAE during the entire study period will be reported. The number and percentage of participants with AESIs, MAAEs, AEs/SAEs, and ARs/SARs leading to withdrawal from the study or discontinuation of the treatment will be tabulated.

The number and percentage of participants with any SAE, AESIs, MAAEs, ARs/SARs leading to withdrawal from the study between Day 57 (28 days post second injection) to Day 168 and from 28 days after 3rd vaccination up to Day 365 will also be summarised by treatment group.

All laboratory test results, and vital signs measurements will be summarised for each treatment group using descriptive statistics at each visit for observed and change from baseline values. The incidence of treatment-emergent abnormal laboratory values will also be summarised using descriptive statistics.

Further details will be provided in the SAP.

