4.3. Changes to Analysis from Protocol

There are no changes to analyses from protocol.

Document: \\dccar2dnetvnasc01p-lan1.quintiles.net\cp_ops\BIOS\MinervaX\GBS-NN_NN2\MVX0006\Biostatistics\Documentation\SAP

Author: [REDACTED] Version Number: 1.0

Version Date: 19APR2024

Template No.: CS_TP_BS016 Revision 7

Reference: CS_WI_BS005

Effective Date: 01Nov2021

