7.5. Baseline

Baseline is defined as the last scheduled non-missing measurement taken prior to dosing and will correspond to Day 1 pre-dose for immunogenicity assessments, clinical laboratory evaluations and vital signs. However, if a subject is missing the planned baseline collection, the previous non-missing scheduled evaluation will become the baseline value.

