7.6. Retests, Unscheduled Visits and Early Termination Data

Unscheduled measurements will not be included in summary statistics. Early termination results will be recorded as such and included with the end-of-study summaries.

Listings will include all scheduled, unscheduled, retest and early discontinuation data.

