17.1. Adverse Events

Adverse Events (AEs) will be coded using MedDRA central coding dictionary, Version 26 or higher.

Treatment emergent adverse events (TEAEs) are defined as AEs that started or worsened in severity on or after the first dose of study medication.

The number and percentage of participants with at least 1 solicited AE (local, systemic and any) during the 7-day solicited period will be tabulated by treatment group with exact 95% CI after each vaccination and overall.

The number and percentage of participants reporting individual solicited local and systemic AE during the 7-day solicited follow-up period will be tabulated by treatment group and severity grade with exact 95% CI as follows:

- Over the 3 doses, the percentage of subjects with the symptom and its exact 95% CI
- At each study dose (visit), the percentage of subjects with the symptom and its exact 95% CI

Counting rules for occurrences of solicited adverse events: When the occurrences of solicited adverse events are summarized, each event recorded as having occurred during a specific period will be counted as only one occurrence regardless of the number of days on which it occurred. For a given participant and the analysis of solicited symptoms within 7 days post-vaccination, missing or non-evaluable measurements will not be replaced. Therefore, the analysis of the solicited AEs includes only vaccinated subjects for doses with documented safety data (i.e., diary completed). More specifically the following rules will be used:

- Participants who documented the absence of a solicited symptom after one dose will be considered not having that symptom after that dose.
- Subjects who documented the presence of a solicited symptom and fully or partially recorded daily measurement over the solicited period will be included in the summaries at that dose and classified according to their maximum observed daily recording over the solicited period
- Subjects who documented the presence of a solicited symptom after one dose without having recorded any daily measurement will be assigned to the lowest intensity category at that dose (i.e. 38°C for fever or

Document: \\dccar2dnetvnasc01p-lan1.quintiles.net\cp_ops\BIOS\MinervaX\GBS-
NN_NN2\MVX0006\Biostatistics\Documentation\SAP

Author: [REDACTED] Version Number: 1.0

Version Date: 19APR2024

Template No.: CS_TP_BS016 Revision 7

Reference: CS_WI_BS005

Effective Date: 01Nov2021

grade 1 for other symptoms)

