17.3.1. Laboratory Reference Ranges

Quantitative laboratory measurements will be compared with the relevant laboratory reference ranges and categorized as:

- Low: Below the lower limit of the laboratory reference range.
- Normal: Within the laboratory reference range (upper and lower limit included).
- High: Above the upper limit of the laboratory reference range.

Document: \\dccar2dnetvnasc01p-lan1.quintiles.net\cp_ops\BIOS\MinervaX\GBS-
NN_NN2\MVX0006\Biostatistics\Documentation\SAP

Author: [REDACTED] Version Number: 1.0

Version Date: 19APR2024

Template No.: CS_TP_BS016 Revision 7

Reference: CS_WI_BS005

Effective Date: 01Nov2021

Clinical laboratory reference/normal ranges will be listed.

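### The SAP's laboratory abnormality count drops the protocol's treatment-emergent condition without declaring the change

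*SAP*

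**What the plan says.** Protocol section 9.4.1 commits to a baseline-referenced output: "The incidence of treatment-emergent abnormal laboratory values will also be summarised using descriptive statistics".

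SAP section 17.3 lists the laboratory summaries. The one on abnormality reads "Incidence of abnormal values according to normal range criteria". The other two are observed values with change from baseline by visit, and a listing of out-of-range results. SAP section 17.3.1 gives the classification rule: "Quantitative laboratory measurements will be compared with the relevant laboratory reference ranges and categorized as" low, normal or high. The participant's baseline category plays no part in it.

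The SAP defines treatment emergence for adverse events only; these "are defined as AEs that started or worsened in severity on or after the first dose of study medication" (section 17.1). It does have a baseline that could serve for laboratory data (section 7.5): "Baseline is defined as the last scheduled non-missing measurement taken prior to dosing". Section 4.3 states: "There are no changes to analyses from protocol".

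**The concern.** The two documents describe different quantities. A treatment-emergent incidence counts participants whose value became abnormal after dosing. A normal-range incidence counts participants whose value is abnormal, whenever that began. A programmer who follows the SAP as written would produce the second, and the section meant to record departures says there are none.

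The difference matters because participants can enter the trial with out-of-range results. Exclusion criterion 3 removes only screening values that the investigator considers clinically significantly abnormal. Participants are 55 to 75 years old, and Cohorts 3 and 4 enrol obese people and people treated for type 2 diabetes. Safety is the primary objective, and protocol section 8.2 names laboratory tests among the safety assessments. A table in which old and new abnormalities cannot be told apart is less informative than the one the protocol planned.

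**Working it through.** **Text comparison**

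| Item | Protocol 9.4.1 | SAP |
|---|---|---|
| Condition for being counted | Abnormal and treatment-emergent | Outside the normal range (17.3, 17.3.1) |
| Use of baseline in the count | Implied by treatment-emergent | None stated |
| Definition of treatment-emergent for laboratory values | Details left to the SAP | None; the definition in 17.1 covers adverse events |
| Baseline-to-post-dose category shift | Not promised | Not planned |
| Departure declared | Not applicable | None (4.3) |

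This mismatch rests on no assumption.

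**Group sizes.** From the 4:1 allocation (protocol 9.2) and the pooling of placebo (SAP 7.2):
- Healthy: 30 × 4/5 = 24 per dose level; pooled placebo 6 + 6 = 12.
- Obese and/or diabetic: 15 × 4/5 = 12 per dose level; pooled placebo 3 + 3 = 6.
- Total: 24 + 24 + 12 + 12 + 12 + 6 = 90.

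**Illustration of size.** The documents state no figure for this quantity, so there is none to reproduce. For one analyte, let
- b = probability of being out of range at baseline,
- s = probability that such a value is still out of range after dosing,
- t = probability of a new out-of-range value in someone normal at baseline.

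All three are assumptions. As shares of the whole group:
- SAP rule = b·s + (1 − b)·t
- New onset = (1 − b)·t
- Pre-existing share of those counted = b·s / [b·s + (1 − b)·t]

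With s = 0.8 and t = 0.05:

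| b | SAP rule | New onset | Pre-existing share |
|---|---|---|---|
| 5% | 0.04 + 0.0475 = 8.8% | 4.8% | 46% |
| 10% | 0.08 + 0.045 = 12.5% | 4.5% | 64% |
| 20% | 0.16 + 0.04 = 20.0% | 4.0% | 80% |

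In a group of 12 with b = 20%, that is 12 × 0.20 = 2.4 participants counted, of whom 12 × 0.04 = 0.5 are new.

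Doubling new onset to t = 0.10, with s still 0.8, gives 13.5% against 9.5%, 17.0% against 9.0%, and 24.0% against 8.0%. The pre-existing shares fall to 30%, 47% and 67%.

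**How often this would arise.** The chance that a group has at least one participant out of range at baseline on a given analyte is 1 − (1 − b)^n:

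| b | n = 24 | n = 12 | n = 6 |
|---|---|---|---|
| 5% | 71% | 46% | 26% |
| 10% | 92% | 72% | 47% |

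Even at low assumed rates, pre-existing abnormalities would often enter the count.

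**The case against.** The strongest reply is that the SAP is brief on this point and does not say the opposite of the protocol. The bullet does not label its count as post-vaccination. It does not say whether counting is per visit or per participant, or whether Day 1 pre-dose is shown. SAP section 9 leaves format and content to table templates that are not among the documents. A by-visit table with a Day 1 row would at least show baseline prevalence. This stands as a limit on the consequence: inclusion of pre-existing values follows from the literal rule, and the SAP does not announce it. It does not remove the mismatch, because the SAP text contains no treatment-emergent condition.

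The plan also has other safeguards: randomised placebo groups pooled within each population, change-from-baseline summaries, and a listing of out-of-range results. Clinically significant laboratory changes must be recorded as adverse events (protocol 8.2.3), and unsolicited events within 28 days of a dose are tabulated. A reader might infer that the trial could not show a laboratory effect of the vaccine. These safeguards mean the documents do not support that. They still do not supply the promised incidence. Mean changes can hide individual shifts, a listing gives no rate, and with 12 and 6 placebo participants a chance imbalance at baseline need not average out.

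A reader might also link this to SAP section 7.6: "Unscheduled measurements will not be included in summary statistics". That rule does keep abnormalities first seen at an unscheduled draw out of the table. However, the protocol never promised to include such values, the listings show them, and the adverse event route remains open. It is a design choice and not a conflict between the documents.

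Finally, laboratory abnormality is not a named primary or secondary endpoint, and no safety comparisons between groups are planned. This is fair, and it limits the weight of the point.

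**Conclusion.** The point holds as an undeclared difference between protocol and SAP in a descriptive safety table. The protocol's treatment-emergent condition is missing from SAP 17.3 and 17.3.1, and SAP 4.3 does not disclose the loss. Followed literally, the SAP would count abnormalities present before dose 1 together with new ones.

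The size is not known from the documents. Under the assumed 80% persistence and 5% new onset, the SAP rule gives about 1.8 to 5 times the new-onset rate as baseline abnormality rises from 5% to 20% (8.8/4.8 to 20.0/4.0). With 10% new onset the ratio is about 1.4 to 3 (13.5/9.5 to 24.0/8.0).

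Two further readings should be avoided. Every out-of-range value would be too broad, because unscheduled measurements and tests not required by the protocol stay out of the summaries. Two of the four cohorts are obese and/or diabetic, but they hold 30 of 90 participants, so the problem should not be described as affecting half the trial.

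**What to change.** In SAP 17.3, define a treatment-emergent laboratory abnormality relative to the SAP 7.5 baseline: normal at baseline and low or high at a scheduled post-dose visit, or a change from low to high or high to low. Tabulate the number and percentage by treatment group, per analyte. The denominator should be participants with a baseline and at least one post-baseline value. State whether the count is per visit, over all post-dose visits, or both.

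This definition does not capture a value that moves further out of range in the same direction. The change-from-baseline summary and the listing remain the place to see that.

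A low/normal/high shift summary from baseline would be a useful option, but neither document promises it. Whether unscheduled values enter the table should be stated, as a secondary choice.

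If the sponsor prefers to keep the normal-range count alone, SAP 4.3 should declare and justify the departure.

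The cost is a short SAP amendment and a modest amount of extra programming across the analytes, more if the shift summary is added. The data needed are already collected.

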17.3.1. Laboratory Reference Ranges

Quantitative laboratory measurements will be compared with the relevant laboratory reference ranges and categorized as:

- Low: Below the lower limit of the laboratory reference range.
- Normal: Within the laboratory reference range (upper and lower limit included).
- High: Above the upper limit of the laboratory reference range.

Document: \\dccar2dnetvnasc01p-lan1.quintiles.net\cp_ops\BIOS\MinervaX\GBS-
NN_NN2\MVX0006\Biostatistics\Documentation\SAP

Author: [REDACTED] Version Number: 1.0

Version Date: 19APR2024

Template No.: CS_TP_BS016 Revision 7

Reference: CS_WI_BS005

Effective Date: 01Nov2021

Clinical laboratory reference/normal ranges will be listed.

17.4. Vital Signs

The following Vital Signs measurements will be reported for this study:

- Resting Systolic and Diastolic Blood Pressure (mmHg) and Pulse Rate (bpm)
- Oral body temperature (°C)

The following summary will be provided for vital signs data:

- Observed and change from baseline by visit for each treatment

17.5. Physical Examination

Physical exam dates will be listed only. New abnormalities occurring after administration of study medication that are clinically significant will be recorded as adverse events.

18. DATA NOT SUMMARIZED OR PRESENTED

The other variables and/or domains not summarized or presented are:

- Comments

These domains and/or variables will not be summarized or presented, but will be available in the clinical study database, SDTM and/or ADaM datasets.

Document: \\dccar2dnetvnasc01p-lan1.quintiles.net\cp_ops\BIOS\MinervaX\GBS-
NN_NN2\MVX0006\Biostatistics\Documentation\SAP

Author: [REDACTED] Version Number: 1.0

Version Date: 19APR2024

Template No.: CS_TP_BS016 Revision 7

Reference: CS_WI_BS005

Effective Date: 01Nov2021

APPENDIX 1. PROGRAMMING CONVENTIONS FOR OUTPUTS

Dates & Times

Depending on data available, dates and times will take the form yyyy-mm-ddThh:mm:ss.

Spelling Format

English UK

Presentation of Treatment Groups

For outputs, treatment groups will be represented as follows and in the given order:

Treatment Group	For Tables and Figures	For Listings (include if different to tables)
Healthy Older Adult GBS-NN/NN2 50 µg	HOA GBS-NN/NN2 50 µg	
Healthy Older Adult GBS-NN/NN2 125 µg	HOA GBS-NN/NN2 125 µg	
Healthy Older Adult Placebo	HOA Placebo	
Obese and/or Diabetic Older Adult GBS-NN/NN2 50 µg	O/DOA GBS-NN/NN2 50 µg	
Obese and/or Diabetic Older Adult GBS-NN/NN2 125 µg	O/DOA GBS-NN/NN2 125 µg	
Obese and/or Diabetic Older Adult Placebo	O/DOA Placebo	

Listings

All listings will be ordered by the following (unless otherwise indicated in the template):

- Participating category (healthy old adults vs obese/diabetic old adults), randomized treatment group (or treatment received if it's a safety output), first by active dose [by ascending treatment dose group] and then placebo,
- Center-subject ID,
- Date (where applicable),

Document: \\dccar2dnetvnasc01p-lan1.quintiles.net\cp_ops\BIOS\MinervaX\GBS-NN_NN2\MVX0006\Biostatistics\Documentation\SAP

Author: [REDACTED] Version Number: 1.0

Version Date: 19APR2024

Template No.: CS_TP_BS016 Revision 7

Reference: CS_WI_BS005

Effective Date: 01Nov2021

- For listings where non-randomized subjects are included, these will appear in a category after the randomized treatment groups labeled 'Not Randomized'.

Document: \\dccar2dnetvnasc01p-lan1.quintiles.net\cp_ops\BIOS\MinervaX\GBS-
NN_NN2\MVX0006\Biostatistics\Documentation\SAP

Author: [REDACTED] Version Number: 1.0

Version Date: 19APR2024

Template No.: CS_TP_BS016 Revision 7

Reference: CS_WI_BS005

Effective Date: 01Nov2021

Electronic Signature Manifestation

This page is a manifestation of the electronic signature(s) used in compliance with the organization's electronic signature policies and procedures.

Signer Full Name	Meaning of Signature	Date and Time
[REDACTED]	Document Approval (I certify that I have the education, training and experience to perform this task)	23 Apr 2024 08:45:14 UTC
[REDACTED]	Document Approval (I certify that I have the education, training and experience to perform this task)	23 Apr 2024 08:49:09 UTC
